13.1.6. Appendix F Study Exit Form

Study Exit

1	1. Please rate your overall experience with the test product.										
Poo		1	2	3	4	5 Neutral	6	7	8	9	10 Excellent
1	a. W	/hy? (1	ree re	sponse)							
2. Do you feel that the test product helped with your cold?											
Not a		1	2	3	4	5 Neutral	6	7	8	9	10 definitely
3. How likely are you to recommend the test product to your friends or family members?											
Not 1		1 ly	2	3	4	5 Neutral	6	7	8	9	10 Extremely Likely
4. Do you feel that the test product helped your body cope with the elements?											
Not a		1	2	3	4	5 Neutral	6	7	8	9	10 definitely

5. Is there anything else that you would like to let us know about your experience with the product (taste, smell, consistency, or other)? $(y/n) \rightarrow$ (free response)

13.1.7. Appendix G Adverse Event Form

Immune AE document

- 1. Did you experience any side effects after taking the test product? Y/N
 - a. If so, did you experience any of the following
 - o itching, rash, hives, throat/lip/tongue swelling, wheezing
 - low blood pressure, fainting, chest pain, shortness of breath, palpitations, irregular heart beat
 - o severe, persistent nausea, vomiting, diarrhea, or abdominal pain
 - o difficulty urinating, decreased urination
 - o fatigue, appetite loss, yellowing skin/eyes, itching, dark urine
 - severe joint/muscle pain
 - o slurred speech, one-sided weakness of face, arm, leg, vision
 - o abnormal bleeding from nose or gums
 - o blood in urine, stool, vomit,
 - o marked mood, cognitive, or behavioral changes, thoughts of suicide
 - o Other:
- 2. Please give a description of the event
- 3. How soon after taking the test product did you experience the side effect?
- 4. What did you do to alleviate the side effect?
- 5. Did you have to go to the hospital or see a doctor for this side effect?
 - a. Please describe any diagnosis or treatment that they provided.
 - b. If you were seen in the hospital, please upload any discharge paperwork or other documents from the hospital.

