- Participant will take the test product twice a day, at least 4-6 hours apart.
- The next day the participant will complete their symptom diary prior to taking the test product. Once completed they will mix 1 packet of the test product into 6-8 oz of water and consume the whole drink. They will take the test product again 4-6 hours later.
- The participant will complete this process daily until their cold symptoms resolve or for 18 days, whichever is shorter.
- If the participant takes ibuprofen or acetaminophen at any time, the participant will record this on their symptom diary.
- After taking the test product, the participant will be instructed to fill out an Adverse Event form for any side-effects experienced.
- The participant will be prompted, by email, to complete the study exit form once the participant's symptoms resolve completely or after 18 days, whichever is shorter.
- Neither the sponsor nor Hawthorne Effect, Inc. will make any attempt to collect any unused test product.
- Upon receipt of study exit survey and review of completed study forms, participant will receive an Amazon gift card of \$25 via email.

6.2.Study Schedule of Activities

Assessments	Screening	Consent	Before Receipt of Test Product	Product Received	Event Start Date**	Days 1-18*	Study Exit***
Study Window							
Screening Survey	Х						
Consent		Х					
Baseline Survey			х				
Demographics			х				
Acknowledgement of Receipt of Test Product				Х			
Test Product Consumed****					Х	Х	
Symptom Diary					Х	Х	Х
Meds & Supplements			Х				
AE Assessment					Х	Х	Х
Study Exit Survey							Х

^{*}Participant will participate in the study starting on the day of the cold until the cold symptoms resolve or 18 days whichever is shorter.

^{**} The day the participant experiences 2 or more of the protocol defined symptoms

^{***} The participant will exit the study at the time of complete cold symptom resolution, 18 days after the start of cold symptoms, or at 90 days if no cold is experienced by the participant.

^{****} The product will be consumed twice a day, 4-6 hours apart

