6.4. Adverse Event and Safety Monitoring

Adverse Events (AEs) are defined as any untoward medical occurrences described by the study participant. All AEs will be self-reported and documented on the platform. The AEs will be reviewed by the study team including the remote trial coordinator and study principal investigator and reported according to the IRB requirements. Participants who experience adverse events will be advised to stop taking the test product and seek medical attention.

In the event that a participant experiences an adverse event, the clinical study manager or clinical ops coordinator will notify both the PI and Sponsor. The Sponsor will take appropriate action according to their standard operating procedures for any adverse events that warrant action by the sponsor.

6.4.1.Anticipated Adverse Events

Anticipated Adverse Events are complications that are known to be associated with the test product (in high doses exceeding recommended use):

- epigastric pain
- nausea
- vomiting
- loss of appetite
- abdominal cramps
- diarrhea
- headaches

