6.4.2. Adverse Event Relationship

Each reported AE will be assessed by the Investigator for relatedness, severity and causality.

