13.1.5. Appendix E Symptom Diary

Daily Symptom Survey

BEFOREtaking the test product OR any allowed medication, please answer all of the following questions daily for the duration of your cold symptoms.

REMINDER: DURING THE TRIAL, YOU ARE NOT ALLOWED TO TAKE ANY COLD MEDICATIONS (NYQUIL/DAYQUIL, TYLENOL COLD, COUGH SYRUP/LOZENGES, ETC.)

1. Cough			
0	1	2	3
No Symptom	Slight	Moderate	Severe
2. Hoarseness			
0	1	2	3
No Symptom	Slight	Moderate	Severe
3. Muscle aches			
0	1	2	3
No Symptom	Slight	Moderate	Severe
4. Runny Nose			
0	1	2	3
No Symptom	Slight	Moderate	Severe
5. Nasal Congestion			
0	1	2	3
No Symptom	Slight	Moderate	Severe
6. Scratchy Throat			
0	1	2	3
No Symptom	Slight	Moderate	Severe

7. Sore throat

0	1	2	3
No Symptom	Slight	Moderate	Severe
8. Sneezing			
0	1	2	3
No Symptom	Slight	Moderate	Severe

- 9. Did you take any pain/fever reducer (ibuprofen/acetaminophen today? (Y/N)
 - a. Why?
 - b. Did it work? (Y/N)
- 10. Have you taken any other cold medications (Nyquil, Dayquil, other cold medication, cough drop, cough syrup, etc.)? (Y/N)
 - a. If yes, please exit from the study
- 11. Have you seen a doctor for your symptoms? (Y/N)
 - a. If yes, were you prescribed anything? $(Y/N) \rightarrow$ if yes please exit from the study
- 12. Did you experience any side effects after taking the product? (Y/N)
 - a. If yes, please fill out the Adverse Event form.

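### Adverse events are defined without regard to cause, but the diary, the adverse event form and its instruction ask only for side effects, so the summary will tend to undercount by the protocol's own definition

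*Combined protocol and SAP*

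**What the plan says.** Section 6.4 gives the definition: "Adverse Events (AEs) are defined as any untoward medical occurrences described by the study participant". The participant is named as the source, and no link to the product is required. The same section adds that "All AEs will be self-reported and documented on the platform". Section 6.4.2 then assigns the judgement of cause: "Each reported AE will be assessed by the Investigator for relatedness, severity and causality".

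The collection tools use a narrower term. Section 6.1 states that, after taking the product, "the participant will be instructed to fill out an Adverse Event form for any side-effects experienced". Diary item 12 (Appendix E) asks "Did you experience any side effects after taking the product", and a yes sends the participant to the adverse event form. Item 1 of that form (Appendix G) asks "Did you experience any side effects after taking the test product", followed by a checklist, an Other line and an open description.

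The schedule in Section 6.2 marks an adverse event assessment at event start, on Days 1-18 and at study exit. The exit form (Appendix F) contains no adverse event question. The adverse event summary is listed among the secondary endpoints in the synopsis and in Sections 3 and 7.1.

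**The concern.** A definition that ignores cause needs a question that ignores cause. Calling something a side effect invites the participant to decide that the product was responsible. Someone who thinks a headache came from the cold or from poor sleep can truthfully answer no, and the event then does not enter the adverse event data. Relatedness, which Section 6.4.2 reserves for the investigator, has in part been settled beforehand by a layperson.

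There is little to catch what is missed. Participants visit no clinic (Section 4), and Section 11 concedes that nobody medically reviews the symptoms. At stake are a listed secondary endpoint, the sponsor notification and study-team review described in Section 6.4, and the use of these data to plan a possible two-arm trial. The primary endpoint is not affected by the mismatch itself.

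**Working it through.** **Step 1: definition against question.**

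| Place | What it covers | Does the wording imply the product as cause? |
|---|---|---|
| Section 6.4, definition | any untoward occurrence the participant describes | no |
| Section 6.4.2, review | each reported event; relatedness judged by the investigator | no, cause is judged afterwards |
| Section 6.1, instruction | side effects | yes |
| Appendix E, item 12 | side effects after the product | yes |
| Appendix G, item 1 | side effects after the product | yes |
| Appendix F, exit form | no adverse event question | not applicable |

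Every side effect is an adverse event, but not every adverse event is a side effect. The solicited set is therefore contained in the defined set, and a count from these tools falls short whenever an unattributed event goes unmentioned. The diary is also scheduled at exit, so the exit assessment could be met by item 12, but that item uses the same wording.

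**Step 2: the seven anticipated events of Section 6.4.1 against the Appendix G checklist.**

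| Anticipated event | Appendix G |
|---|---|
| nausea, vomiting, diarrhea | in the item "severe, persistent nausea, vomiting, diarrhea, or abdominal pain" |
| epigastric pain, abdominal cramps | nearest match is abdominal pain, in the same item |
| loss of appetite | named, no severity qualifier |
| headaches | not named |

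Five of the seven sit in the item that opens with a severity qualifier, one is unqualified and one is absent (5 + 1 + 1 = 7). Headache is also not among the eight symptoms scored in the diary. Appendix G has no severity question, although Section 6.4.2 requires the investigator to assess severity.

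**Step 3: size, as illustration only.** The plan states no adverse event rate, so there is no such figure to reproduce. Section 7.2 gives the number treated: 200 × 0.40 = 80, which reproduces its 80. The true proportion p and the capture share c (the fraction of affected participants whose event is reported as a side effect) are assumptions. Expected recorded cases = 80 × p × c:

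| True p | c = 100% | c = 75% | c = 50% | c = 25% |
|---|---|---|---|---|
| 5% | 4 | 3 | 2 | 1 |
| 10% | 8 | 6 | 4 | 2 |
| 20% | 16 | 12 | 8 | 4 |

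The chance of recording at least one case is 1 − (1 − pc)^80. At p = 5% it is 0.983 with full capture, 0.953 at 75%, 0.868 at 50% and 0.634 at 25%.

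Exact 95% intervals for some of these counts:
- True 20%, c = 50%: 8/80 = 10%, interval 4.4% to 18.8%, which excludes 20%.
- True 20%, c = 75%: 12/80 = 15%, interval 8.0% to 24.7%, which includes 20%.
- True 10%, c = 50%: 4/80 = 5%, interval 1.4% to 12.3%, which includes 10%.
- True 5%, c = 50%: 2/80 = 2.5%, interval 0.3% to 8.7%, which includes 5%.

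The expected count falls under any incomplete capture. Whether the reported interval misses the truth depends on values the documents do not supply.

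**The case against.** Several points on the other side are fair.

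- **The form is not confined to severe events.** A reader might infer that it is. Only the gut and joint/muscle items say severe, and the mood item says marked. Others carry no such qualifier, for example "itching, rash, hives, throat/lip/tongue swelling, wheezing". In the gut item the qualifier could even be read as applying to nausea alone. The Other line and the open description accept mild events. This stands, but these entries sit behind or after the side-effect question and do not remove that filter.
- **The investigator is not cut off from every other event.** A reader might infer that unattributed events are never judged. They could surface through diary item 9a (the reason for taking a pain or fever reducer), item 11 (doctor visits), the exit form's free text or coordinator contact. This stands. None of these asks for adverse events, so the accurate statement is that there is no solicited route.
- **The question is partly about timing.** It says after taking the product, and Appendix G item 3 asks how soon after. Participants may not apply a strict causal test. This limits how confidently the loss can be sized; the mismatch in wording remains.
- **Section 6.4.1 ties its list to high doses exceeding recommended use.** That is a reason not to expect many such events. Since the protocol names them as anticipated, the form should still be able to record them.
- **Not everything is visible.** Consent pages are absent from the public file, and the cold start form does not appear in the text available. The finding rests on the forms and instructions that can be read.
- **A broader question has consequences.** Every respondent has a cold, so an open question would collect cold symptoms unless told otherwise. Sections 2.2.3 and 6.4 also advise participants with adverse events to stop the product. This stands and shapes the fix.

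**Conclusion.** The mismatch is real and can be read directly from Sections 6.1, 6.4 and 6.4.2 and Appendices E, F and G. Followed as written, the plan will tend to undercount adverse events against its own definition, because unattributed events are not asked for and the investigator's assessment covers reported events only. The checklist adds to this: milder gut events, and headache at any severity, depend on the Other line or the open description.

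The direction rests on one modest assumption, that some participants will not report as a side effect an event they do not blame on the product. The size is unknown. It is tempting to conclude that the reported rate would be halved, or that its confidence interval would exclude the truth. The documents do not support either; the second holds at an assumed 20% with 50% capture and fails at 75%. Nor does the plan commit to any tolerability claim; it promises only a summary. The point is worth correcting because it concerns a listed secondary endpoint, but it does not undermine the primary analysis.

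**What to change.** 1. In the Section 6.1 instruction, diary item 12, Appendix G item 1 and the exit form, ask about any new or worse health problem other than the cold symptoms already scored in the diary, whether or not the participant thinks the product caused it. State how events near that boundary are handled: fever is a cold-onset criterion without a scored diary item, and muscle pain appears in both the diary and Appendix G.
2. List the seven anticipated events of Section 6.4.1 at any severity, each with a mild, moderate or severe grade.
3. Add a separate item for the participant's own view of cause, and leave relatedness to the investigator.
4. Reconcile the stop-product text in Sections 2.2.3 and 6.4 with the broader question. More recorded events under the present text could mean more stopped treatment and more exits, and Section 7.3 censors withdrawals. Exposure and censoring in the primary analysis should not change as an unintended result of rewording a form.

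The cost is revised forms, some added review work, a higher reported adverse event rate and the reconciliation in step 4. If the forms cannot change, label the summary participant-attributed side effects, not adverse events, and describe it that way wherever it is reported.
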